Isokinetic dynamometry, most commonly performed using systems such as the Biodex, is considered the gold standard for assessing quadriceps and hamstring performance. It provides dynamic, objective, and reproducible measures of torque during concentric and eccentric contractions under controlled angular velocities (**Drouin et al., 2004**). In addition to peak torque, this method yields further performance parameters including total work, power, and fatigue index that offer a comprehensive understanding of muscular capacity (**Impellizzeri & Marcora, 2009**).

A distinct advantage of isokinetic dynamometry lies in its ability to assess the H:Q ratio. The conventional H:Q ratio is defined as the relationship between concentric hamstring and concentric quadriceps peak torque, whereas the functional H:Q ratio compares eccentric hamstring to concentric quadriceps torque (**Aagaard et al., 1998**). These indices are valuable for evaluating muscular balance across the knee joint, informing injury risk assessment,

rehabilitation progress, and return-to-sport readiness (Coombs & Garbutt, 2002).

The validity of isokinetic dynamometry is well established. Torque is measured directly via the device's lever arm at predefined angular velocities, demonstrating strong criterion validity in comparison with other strength assessment methods. Furthermore, the ability to isolate joint movements and regulate contraction speed enhances construct validity, making it particularly suitable for both clinical practice and research applications (Feiring et al., 1990).

Reliability has been consistently confirmed across studies. Test-retest reliability of isokinetic quadriceps and hamstring strength has shown excellent results, with ICCs ranging from 0.85 to 0.99 depending on contraction mode and angular velocity (Maffiuletti et al., 2007; Impellizzeri & Marcora, 2009). H:Q ratio measurements similarly demonstrate strong reproducibility, with ICCs typically reported between 0.82 and 0.95 (Ayala et al., 2012). The standard error of measurement (SEM) for peak torque generally falls between 5–8%, indicating minimal variability due to measurement error (Dirnberger et al., 2012). Moreover, Biodek dynamometers have demonstrated high inter-device reliability, ensuring consistent outcomes across different testing sites (Feiring et al., 1990).

- **Assessment of range of motion ROM:**

Range of motion (ROM) assessment of the knee joint is commonly performed using different clinical and laboratory-based tools, with the goniometer being the most widely applied method in both research and clinical practice. The universal goniometer is inexpensive, portable, and easy to use, making it a gold standard in routine physiotherapy assessments. Previous studies have shown that the universal goniometer demonstrates excellent intra-

rater reliability, with intraclass correlation coefficients (ICC) ranging from 0.90 to 0.99 for knee flexion and extension (**Brosseau et al., 2001**). Inter-rater reliability has also been reported as high, with ICC values between 0.85 and 0.95, depending on examiner experience (**Gogia et al., 1987**). Its validity in comparison to radiographic measurements has been established, showing strong correlations ($r = 0.93\text{--}0.97$) between goniometric and radiographic values for knee joint angles (**Sadeghi et al., 2015**).

Digital inclinometers and smartphone-based goniometric applications have been introduced as alternatives. Digital inclinometers have demonstrated excellent intra-rater reliability (ICC = 0.97) and inter-rater reliability (ICC = 0.94) for knee flexion measurements, with validity coefficients up to $r = 0.96$ compared to radiographic standards (**Kolber & Hanney, 2012**). Smartphone-based applications have also shown promising results, with studies reporting ICC values of 0.85–0.95 for knee ROM compared to the universal goniometer. These emerging tools provide greater accessibility, although they remain complementary rather than replacements for traditional goniometry in clinical trials (**Ockendon & Gilbert, 2012**).

Radiographic imaging and 3D motion analysis systems are considered reference standards for ROM assessment, particularly in research contexts. Radiographic assessment demonstrates nearly perfect validity, as it directly visualizes joint angles; however, its practicality is limited by cost and radiation exposure. Three-dimensional motion capture systems, though resource-intensive, have been reported to achieve validity coefficients above 0.95 compared to radiographic assessment, and inter-rater reliability exceeding 0.90 for dynamic knee ROM. Despite these advances, goniometry remains the most practical and reliable method in routine clinical and sports settings due to its balance between validity, reliability, and accessibility (**Windolf et al., 2008**).

CHAPTER III

SUBJECTS, MATERIALS AND METHODS

The current study aims to investigate whether incorporating mini squat exercises at different knee flexion angles into a leg press training program enhances hamstring- quadriceps ratio H:Q ratio in football players.

Design of the study:

This study will follow a randomized controlled trial (RCT) design.

Study setting

The study will be conducted at the outpatient physical therapy clinic of Jazan University Hospital, kingdom of Saudi Arbia.

Sample size:

The sample size for this study was determined using G*Power version 3.1.9 (Heinrich-Heine-University, Düsseldorf, Germany). An a priori power analysis was conducted for a repeated measures MANOVA with between-subject factors, setting the alpha level (α) at 0.05, desired power ($1 - \beta$) at 0.80, Pillai's trace (V) at 0.1989, and effect size $f^2(V)$ at 0.2877, targeting isometric muscle strength across four independent groups. The analysis indicated a minimum required sample size of 48 participants, allocating 12 per group. To compensate for possible dropouts, the total sample was increased to 60 participants, with 15 individuals per group (**Wirth et al., 2016**) (figure 3).

[figure not shown]

Fig 3:sample size calculation using G power

Randomization, allocation concealment, and blinding

The enrolled participants will be randomized in a simple randomization way using (www.randomizer.org/links/) by another participant not involved in the data collection. Allocation concealment will be ascertained using sealed, opaque, sequentially numbered envelopes. The participants will be blinded to the assigned intervention group.

Participants

Sixty male football players from Al-Ahli and Al-Ittihad football clubs in the Kingdom of Saudi Arabia. Participants will be asked to sign a written informed consent that includes participation in the experimental trial, permission to use data and/or pictures, and informing them of their right to withdraw at any time (**Appendix I**).

Participants will be randomized into 4 equal groups: an experimental group (A, B, and C), and a Control group (D).

Experimental groups (A, B, and C)

Group A: Fifteen participants will receive mini-squat exercises at 30° knee flexion and leg press exercises

Group B: Fifteen participants will receive mini-squat exercises at 45° knee flexion and leg press exercises

Group C: Fifteen participants will receive mini-squat exercises at 60° and leg press exercises

Control group D: Fifteen participants will receive leg press exercise program only.

Inclusion criteria:

Participants having the following criteria will be included in the study:

1. Male football players aged between 18–30 years (**Scoz et al., 2021**).
2. Body Mass Index (BMI) between 18.5 and 24.9 kg/m² (**Walsh et al., 2018 & Sattar& Lean, 2009**).
3. Currently training or playing with a registered football club/team.
4. Hamstring-to-Quadriceps (HQ) strength ratio of ≥ 0.6 (**Çelebi et al., 2018**).
5. Having no oral or injectable non-steroidal anti-inflammatory drugs (NSAID), 2 weeks before starting study.
6. Having no oral injectable corticosteroids 3 months before starting the study.

Exclusion criteria:

Participants having any of the following criteria will be excluded from the study:

1. History of acute or chronic injury to the knee, hip, or ankle joint
2. Undergoing any other rehabilitation or physical therapy programs during the six weeks before starting the study
3. Diagnosed with neurological or systemic disorders affecting muscle function or balance

4. Participation in competitive sports or high-intensity training outside the study protocol during the study period
5. Presence of any contraindication to exercise, such as uncontrolled hypertension or heart conditions.
6. Clinically free from lower limb injuries.
7. Having no history of neurological, cardiovascular, or musculoskeletal disorders.

Instrumentation:

a. Isokinetic dynamometry:

Isokinetic dynamometry (**BiodeX System 4 Pro**) is considered the gold standard for assessing muscle strength and HQ ratios, offering valid and reliable measurements through controlled torque assessment during concentric and eccentric contractions. Its criterion validity is well established, and reliability is consistently high, with ICCs ranging from 0.85 to 0.99. Furthermore, its ability to calculate both conventional and functional H:Q ratios provide a reproducible measure of knee muscle balance, making it highly valuable for evaluating injury risk, rehabilitation outcomes, and return-to-sport readiness (**Ayala et al., 2012**) (figure 4).

Fig 4: Isokinetic dynamometry device (BiodeX System 4 Pro, BiodeX Medical Systems, Inc., Shirley, NY, USA) (adopted from Sinacore et al. 2017).

b. leg press machine (FL1801 Isolateral Leg Press):

Fig 5: Leg press machine (FL1801 Isolateral Leg Press, BodyKore Inc., Garden Grove, CA, USA) (adopted from BodyKore Inc., 2025).

c. Goniometer (Jamar Plus+ Digital 8):

Digital goniometers provide more precise joint range of motion (ROM) measurements than traditional goniometers by offering direct electronic readouts, reducing examiner error. They have demonstrated excellent reliability and validity, with intra-rater ICC values up to 0.96 for knee flexion and 0.92 for extension, and inter-rater ICCs ranging from 0.88 to 0.94. These results highlight their accuracy and reproducibility, making them particularly useful in research and advanced clinical practice (Kolber & Hanney, 2012) (figure 6).

Fig 6: Goniometer (Jamar Plus+ Digital 8" Goniometer, China) (adopted from Jeon et al., 2024).

Assessment procedures:

Participants will be interviewed, and they will be checked for eligibility according to pre-mentioned inclusion criteria. Participants who will be eligible for the study will sign a written consent form, and demographic data regarding height, weight, and BMI will be calculated and recorded. The pretest will be performed 3 days after a familiarization test, which included the same tests in the same order. The same tests will be carried out again 3 days after the last training session.

The assessment procedure will include the following:

1-Measurement of quadriceps strength:

- The participant will be seated on the isokinetic dynamometer chair, with proper posture and alignment ensured.
- The chest, pelvis, thigh, and ankle will be stabilized using adjustable straps to minimize compensatory movements.
- The lateral femoral epicondyle (the anatomical axis of the knee joint) will be aligned with the mechanical axis of the dynamometer arm.
- The lever arm of the dynamometer will be securely attached to the participant's lower leg, just above the ankle, using a padded cuff.

- Test Parameter Settings will be:
 - Mode: Concentric contraction.
 - Velocity: Commonly set at 60°/s for maximal strength.
 - The range of motion (ROM): between 90°knee flexion to full knee extension.
 - Repetitions: 3–5 maximal repetitions.
- The participant will be allowed to perform a submaximal warm-up trial to become familiar with the movement and resistance.
- The participant will be instructed to perform maximal knee extension against the resistance of the device, moving from a flexed to an extended position.
- The test will be conducted unilaterally, assessing one leg at a time.
- The participant will be encouraged to exert maximal effort during each repetition.
- The isokinetic device will record key outcome measures including peak torque (Nm), average power, and total work for each repetition. These values will be used to quantify quadriceps strength (figure 7).

2- Measurement of hamstrings muscle strength:

All previously described quadriceps muscle evaluation procedures will be applied for the hamstrings muscle strength test; however, the range of motion will be set from full knee extension, and the participant will be instructed to actively bend the knee against the resistance of the device to 90°.

3-Hamstring to quadriceps H:Q ratio calculation:

H:Q ratio will be calculated by use this formula:

$$H:Q \text{ Ratio} = \left(\frac{\text{Hamstring Peak Torque (Nm)}}{\text{Quadriceps Peak Torque (Nm)}} \right)$$

- Value interpretation:

- < 0.5: hamstring weakness.
- 0.5-0.7: normal range.
- 0.8-1: strong hamstring.

Fig 7: quadriceps and hamstring muscles strength measurement by isokinetic dynamometer device (adopted from Sinacore et al. 2017).

Treatment procedures:

1) Control group D: The participant will receive 18 sessions of leg press exercise using a leg press machine, conducted over a six-week period. Each training session will consist of 7 sets of 10 repetitions, with inter-set rest intervals of 90 seconds (**Wirth et al., 2016 a)** Before starting the leg press program, a standardized warm-up consisted of 5 min of submaximal cycling on an ergometer and 2 to 3 sets of moderate loaded squats with 6 repetitions each.

10 Repetition Max (10RM) Test:

The 10-repetition maximum (10RM) test will be conducted to determine the initial training load as a following:

- The machine will be loaded with a light weight (approximately 25–30% of the participant's body weight).
- The participant will perform 10 repetitions using proper form.
- The weight will be increased gradually (by 5–10 kg) after each successful attempt.
- This process will continue until the participant reaches a weight they can complete for 10 repetitions with good form, but with difficulty during the final 2 reps.
- That weight will be recorded as the participant's 10 Repetition Maximum (10RM).
- Strength training will then begin at 75–85% of the determined 10RM (**Piper et al., 2021**).

Leg Press Exercise:

1. The seat and backrest of the leg press machine will be adjusted to position the participant's hips and knees at approximately 90 degrees of flexion to ensure a comfortable and standardized starting posture.
2. The participant's feet will be positioned shoulder-width apart on the footplate, with the toes slightly externally rotated and the heels in full contact with the platform.
3. The participant will maintain full contact with the backrest throughout the exercise, with the head and spine supported. The side handles will be grasped to enhance postural stability and balance.

4. The exercise will commence from a flexed knee position, with particular attention given to maintaining proper knee alignment over the feet, avoiding any medial or lateral deviation.
5. The participant will extend the knees and hips to press the platform upward, taking care to avoid full knee lockout at the end of the movement.
6. The platform will then be returned to the initial position in a controlled manner through knee flexion, maintaining proper form throughout the eccentric phase (figure 8).

[figure not shown]

Fig 8: Leg press exercise adopted from (adapted from Martín et al., 2020).

2) Experimental groups: The participant in each subgroup (A, B, and C) will perform the same leg press exercise protocol applied for group D followed by mini squat exercise program with 5 min of submaximal cycling on an ergometer between 2 treatment programs. A total of 18 sessions will be conducted over a six-week period as follows:

1. **Group A:** participants will receive mini-squat program at 30° in addition to leg press program
2. **Group B:** participants will receive mini squat program at 45° in addition to leg press program
3. **Group C:** participants will receive mini-squat at 60° in addition in addition to leg press program

Mini-squat program:

1. Participants will stand barefoot or wear flat training shoes on a stable surface, placing their feet shoulder-width apart with toes slightly pointed outward.
2. A goniometer will be used during the first session to measure the target knee flexion angle (30° for group A, 45° for group B, and 60° for group C) demonstrated once by the examiner on one leg while the participant stands still. This will be followed by passive guidance into the used angles to help the participant recognize the posture and depth, with instructions to remember the sensation for future sessions; goniometer use will be repeated in later sessions only if corrective feedback is required.
3. Mini-squat session will last 10 minutes. Squat will be performed in a slow and controlled manner (approximately 2 seconds down and 2 seconds up), with short rests of 15–30 seconds allowed every 1–2 minutes as needed. Approximately six minutes of active squatting will be completed per session, with the remaining time allocated for brief rests and transitions (**adapted from Hartmann et al., 2016**) (figure 9).

Fig 9: Mini squat exercise (adopted from Prentice, 2024).

Statistical analysis

All analyses were carried out using IBM SPSS Statistics version 27 (IBM Corp., Chicago, IL, USA).

- Subject characteristics will be analyzed using ANOVA, while the Chi-squared test will be used to compare the distribution of the affected side among the groups
- The Shapiro-Wilk test assessed the normality of the data, followed by Levene's test to verify the homogeneity of variances across groups.
- A mixed MANOVA will be conducted to evaluate the effects of group on the dependent variable(s).
- Post-hoc multiple comparisons were performed with Bonferroni correction to adjust for Type I error.
- Statistical significance was determined at a threshold of $p < 0.05$.

REFERENCES

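### The sample-size paragraph gives a Pillai's V and an f²(V) that cannot both hold, and it powers isometric strength, which the trial does not measure

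*Combined protocol and SAP*

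**What the plan says.** The Sample size section states: "An a priori power analysis was conducted for a repeated measures MANOVA with between-subject factors". Alpha is 0.05 and power 0.80. The effect is given twice, first as Pillai's "trace (V) at 0.1989, and effect size" f²(V), and then with the value of the latter, "at 0.2877, targeting isometric muscle strength across four independent groups". The result is: "The analysis indicated a minimum required sample size of 48 participants, allocating 12 per group". This is raised to 60 (15 per group) for dropout. The section refers to Figure 3 for the G*Power output, which is not reproduced in the text available to us.

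Under Assessment procedures, the quadriceps test settings are "Mode: Concentric contraction" and "Velocity: Commonly set at 60°/s for maximal strength", through 90° of knee motion. The outcomes are described so: "The isokinetic device will record key outcome measures including peak torque (Nm), average power, and total work for each repetition". The hamstring test follows the same procedure in the opposite direction, and H:Q is the ratio of the two peak torques. There are two test occasions, a pretest and a post-test: "The same tests will be carried out again 3 days after the last training session". The Statistical analysis section plans a mixed MANOVA with Bonferroni-corrected post-hoc comparisons.

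**The concern.** V and f²(V) are two expressions of the same effect, so either one fixes the other once s is known. If the printed pair does not satisfy the conversion, at least one value or label is wrong, and a reader cannot tell which effect the trial was sized to detect.

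The named outcome adds to this. An isometric test holds the joint still, whereas the described test moves the knee at 60°/s. The purposes and hypotheses name quadriceps strength, hamstring strength and the H:Q ratio, and no isometric test is described for any of them. The paragraph is the plan's only justification for 48 and 60. As it stands, the power claim has no clear effect size and no link to an outcome that will be analysed, which makes a null result hard to interpret.

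**Working it through.** **Inputs.** From the Sample size section: V = 0.1989, f²(V) = 0.2877, alpha 0.05, power 0.80, four equal groups, N = 48 and 60. From Assessment procedures: two occasions. The number of measures and the correlation used in the calculation are not in the readable text, so they are assumptions below.

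**1. Do V and f²(V) agree?** f²(V) = V/(s − V) and, in reverse, V = s·f²/(1 + f²), where s is a whole number no greater than 3 with four groups.

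| s | f²(V) from V = 0.1989 | V from f²(V) = 0.2877 |
|---|---|---|
| 1 | 0.1989/0.8011 = 0.248 | 0.2877/1.2877 = 0.223 |
| 2 | 0.1989/1.8011 = 0.110 | 0.5754/1.2877 = 0.447 |
| 3 | 0.1989/2.8011 = 0.071 | 0.8631/1.2877 = 0.670 |

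No row gives the printed pair. For both to hold, s would have to be 0.1989 × 1.2877/0.2877 = 0.89, which is impossible. Rounding does not explain the gap.

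**2. Can the plan's N = 48 be reproduced?** Read 0.2877 as f. Then 3·f² = 3 × 0.2877² = 0.2483, and V = 0.2483/1.2483 = 0.1989, the printed V. With a noncentral F on 3 and N − 4 degrees of freedom and λ = 3·N·f², power is 79.0% at N = 47, 80.0% at N = 48 and 89.4% at N = 60. The stated V, N and power all follow from this one reading.

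**3. The printed values at face value, s = 1.** The degrees of freedom are the same and λ = N·f²(V).

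| Value taken as correct | N = 48 | N = 60 |
|---|---|---|
| V = 0.1989 (f² = 0.2483) | 80.0% | 89.3% |
| f²(V) = 0.2877 | 86.0% | 93.5% |

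**4. Where does the multiplier of 3 in step 2 come from?** The text does not say. For group-by-time over two occasions the multiplier is 2/(1 − ρ), which is 3 at ρ = 1/3. For a between-groups test on the average of m measures it is m/(1 + (m − 1)ρ). That is 3 at m = 3, ρ = 0, or at m = 6, ρ = 0.2, but with two measures it would need ρ = −1/3. So the printed numbers do not identify the effect that was powered.

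**5. How much does the correlation matter?** Group-by-time, two occasions, f = 0.2877, λ = N·f²·2/(1 − ρ), ρ assumed:

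| ρ | N = 48 | N = 60 |
|---|---|---|
| 1/3 | 80% | 89% |
| 0.5 | 91% | 96% |
| 0.7 | 99% | over 99% |
| 0.8 | over 99% | over 99% |

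**6. Outcome.** The sample-size text targets isometric strength. The assessment text describes concentric knee extension and flexion at 60°/s, and H:Q computed from those peak torques. No effect size is given for any of these.

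**The case against.** The best defence is that this is a wrong symbol and a wrong word. If 0.2877 is f, the calculation is coherent and 48 stands. Isometric may be a slip for isokinetic, or may describe the outcome in the source of the effect size. Because the effect is standardised, changing that word alone alters no number. Figure 3 may show the number of measures and the correlation, so their absence from the readable text cannot be held against the plan. Most of this stands, and it limits the point to a correction of the paragraph. It does not remove the contradiction, because both values are printed in the text.

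A reader might infer three stronger things:

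- **That 48 is too few.** The documents do not support this, since with s = 1 both printed values give at least 80.0% at N = 48.
- **That true power could be near one half.** A three-outcome test with s = 3 gives 50–54% from V and over 99% from f²(V) at N = 48. The Sample size section does not name such a test, so that gap reflects an assumed model.
- **That the Bonferroni comparisons are badly underpowered.** No passage claims 80% for them, and their power depends heavily on an unknown correlation. With six comparisons, 12 per group, f = 0.2877 and equal gains assumed in the three mini-squat arms, arm-versus-control power on pre/post change is 53% at ρ = 1/3 but 92% at ρ = 0.7. The literature review cites test-retest ICCs of 0.85–0.99 for isokinetic strength and 0.82–0.95 for H:Q. These make the higher correlations plausible, although six weeks of training may lower them.

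**Conclusion.** The paragraph is wrong as written on two counts. First, V = 0.1989 and f²(V) = 0.2877 are incompatible for every admissible s. This follows from the definition alone. Second, the outcome named is not one the trial measures, so the stated 80% is not tied to concentric peak torque or to H:Q.

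The numerical effect is modest. Under s = 1 the contradiction is worth 6 percentage points at N = 48 (80.0% against 86.0%) and about 4 at N = 60 (89.3% against 93.5%). The mislabelled-f explanation fits all the printed figures but remains an inference without Figure 3. A sample size of 48 or 60 is not shown to be inadequate. The paragraph should be corrected, but the point does not call the design into question.

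**What to change.** Keep N = 60 and rewrite the Sample size paragraph:

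1. Correct the label or the value so that V and the effect size agree. If 0.2877 was entered as f, say so.
2. State in the text the effect tested (group-by-time over the two occasions), the number of measures and the correlation, copied from Figure 3 if they are there.
3. Replace isometric strength with the measured outcomes: concentric isokinetic peak torque at 60°/s, and H:Q.
4. Restate the power at 48 and 60 for that test. The documents supply no effect size for these outcomes and no pre/post correlation, so give each as a stated assumption with a range, for example ρ from 1/3 to 0.8.
5. Optionally, add that the figure is for the omnibus test and not for the Bonferroni comparisons.

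The cost is protocol wording and one rerun, which needs an assumed or externally sourced effect size. No extra players and no change of procedure are required. The stated power may move in either direction.

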Recent studies have highlighted the importance of exercise selection and angle specificity in resistance training, showing that different knee angles result in varied activation patterns in the quadriceps and hamstrings. However, current literature offers limited insight into the effects of integrating mini squat exercises with leg press training on injury prevention and functional outcomes in athletic populations. In particular, there is a lack of literature on how such a combined leg press and mini squat exercise at different angles influences the H:Q ratio, lower limb neuromuscular control, and performance in young male football players. Therefore, the present study aims to examine whether incorporating mini squats performed at varying knee flexion angles into a leg press training program can improve muscle balance and lower limb strength in football players. The findings may provide valuable guidance for physiotherapists, coaches, and sports scientists in developing evidence-based, angle-specific exercise protocols tailored to the functional demands of athletes. (**Watanabe et al., 2020**).

Delimitation:

This study will be delimited to the following:

1. Male football players aged between 18–30 years (**Scoz et al., 2021**).
2. Body Mass Index (BMI) between 18.5 and 24.9 kg/m² (**Walsh et al., 2018 & Sattar & Lean, 2009**).
3. Participants will receive 18 training sessions, conducted three days per week, over six successive weeks

Basic assumptions:

1. Participants understood and followed the given instructions during assessment and treatment procedures.
2. Participants did not receive any additional medical or physical therapy treatment during the study period.

Hypotheses will be:

1. There is no statistically significant difference between adding 30°, 45°, and 60° knee flexion mini-squat exercises to leg press exercise and leg press exercise alone on quadriceps strength in football players.
2. There is no statistically significant difference between adding 30°, 45°, and 60° knee flexion mini-squat exercises to leg press exercise and leg press exercise alone on hamstrings strength in football players.
3. There is no statistically significant difference between adding 30°, 45°, and 60° knee flexion mini-squat exercises to leg press exercise and leg press exercise alone on the hamstrings-to-quadriceps H:Q ratio in football players.

Definitions of terms

Hamstring-to-quadriceps ratio H:Q ratio:

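### Simple randomisation is specified alongside four arms of exactly 15; read literally it yields 15/15/15/15 in 0.2% of allocations, so the method and the arm sizes must be reconciled before enrolment.

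*Combined protocol and SAP*

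**What the plan says.** - **Method of allocation** (Randomization, allocation concealment, and blinding): "The enrolled participants will be randomized in a simple randomization way using" a named website, "by another participant not involved in the data collection". Concealment is by sealed envelopes numbered in sequence. How many envelopes belong to each arm is not stated.
- **Arm sizes** (Participants): "Participants will be randomized into 4 equal groups". Groups A, B and C are each given fifteen players, and the control group is described the same way: "Control group D: Fifteen participants will receive leg press exercise program only".
- **Sample size**: "The analysis indicated a minimum required sample size of 48 participants, allocating 12 per group"; then, to allow for dropout, "the total sample was increased to 60 participants, with 15 individuals per group".
- **Comparisons of interest** (Hypotheses): the first null hypothesis concerns adding the 30°, 45° and 60° "mini-squat exercises to leg press exercise and leg press exercise alone on quadriceps strength in football players". The second and third repeat this for hamstring strength and the H:Q ratio.
- **Analysis** (Statistical analysis): a mixed MANOVA, and then "Post-hoc multiple comparisons were performed with Bonferroni correction to adjust for Type I error".

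The protocol mentions no blocks, no stratification, no fixed-length list and no rule that closes an arm at 15.

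**The concern.** Simple randomisation, in its usual sense, assigns each player independently of all the others. Arm sizes are then random, and the stated method cannot be relied on to give the stated 15 per arm. The plan allows two readings and does not choose between them.

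1. **Literal.** Assignments are independent and arm sizes are multinomial. The design loses balance that it could have at no cost.
2. **Loose.** The authors intend a prepared list with 15 places per arm in the envelopes. The arm sizes then hold, but the label is wrong and the trial would misreport its allocation method.

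Under the first reading the risk lies mainly in the comparisons with group D. D is the common comparator in all three hypotheses, so a small D weakens all three comparisons together.

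The same sentence has the list prepared by another participant. This is probably a slip for another person, but as written a trial participant would generate the allocation.

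**Working it through.** **Inputs from the protocol.** 60 players, four arms in equal ratio, 15 per arm; 48 players (12 per arm) before the dropout allowance; Pillai's V = 0.1989; alpha 0.05; power 0.80.

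**The plan's own figure.** 48/60 = 0.80, so the step from 48 to 60 implies 20% dropout, and 12/0.80 = 15 per arm. The inflation reproduces. The 20% is implied, not stated. The 12 per group is the equal split of 48; the plan does not set it as a floor for each arm.

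**Arm sizes under independent assignment** (exact multinomial, n = 60, probability 1/4 each):

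- P(15/15/15/15) = 60!/[(15!)^4 × 4^60] = 0.00214, about 1 in 467.
- SD of one arm's size = √(60 × 0.25 × 0.75) = 3.35, with a 95% range of about 9 to 22.
- P(at least one arm below 12, before dropout) = 0.540.
- Expected smallest arm 11.1; expected largest 19.1.
- P(group D below 12) = 0.148.

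**Overall test.** F test with 3 and N − 4 degrees of freedom and effect size f² = V/(1 − V) = 0.1989/0.8011 = 0.2483. This gives power 0.80 at N = 48, which matches the plan's target. At N = 60:

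- 15 per arm: 0.894.
- Simple randomisation, averaged over allocations: 0.878 to 0.888, depending on the pattern of means.

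**Comparisons with D.** The plan states no pairwise effect size, so a reference effect is assumed: the standardised difference with 80% power at 12 versus 12, two-sided, at Bonferroni alpha 0.05/6 (all six pairs). That is d = 1.544. Power is from the noncentral t distribution, with noncentrality d × √[ab/(a + b)] for arms of size a and b.

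| Allocation | Power |
|---|---|
| 15 versus 15 | 0.907 |
| Simple, mean of one comparison with D | 0.882 |
| Simple, mean of the weakest of the three | 0.830 |

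The weakest comparison falls below 0.80 in 25.1% of allocations. At unadjusted alpha 0.05 (d = 1.197) the three powers are 0.886, 0.866 and 0.823, and the weakest is below 0.80 in 25.3%.

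The harmonic mean 2ab/(a + b) gives the same picture without assuming an effect size. At least one comparison with D has an effective arm size strictly below 12 in 25.4% of allocations, and 12 or below in 29.8% (10 versus 15 gives exactly 12).

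**Completers at an assumed 20% dropout.** With 15 per arm, one arm keeps at least 12 with binomial probability 0.648, so P(some arm below 12) = 1 − 0.648^4 = 0.824. The figures for simple randomisation come from 1,000,000 simulated trials.

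| | Exactly 15 per arm | Simple |
|---|---|---|
| Some arm below 12 completers | 82% | 98% |
| Some arm with 9 or fewer | 22% | 69% |
| Expected smallest arm | 10.4 | 8.5 |

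**The case against.** The strongest reply is that the literal reading may not be the intended one. The protocol gives the arm size several times, numbered envelopes fit a prepared list with 15 places per arm, and simple may only mean unblocked and unstratified. The documents do not say whether the website returns equal sets. This stands: the power losses are conditional on the literal reading. The contradiction is not, because under the other reading the method is still misdescribed.

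Other points:

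- **Simple randomisation is unbiased, and the planned analysis can handle unequal arms.** True. No bias is alleged.
- **The only test with a stated power calculation is the MANOVA, and it barely moves.** True. The protocol also states f²(V) = 0.2877, which does not agree with its own V. Using 0.2877 puts power at N = 60 and 15 per arm at 0.917 or 0.935, depending on how the noncentrality is defined, so the reserve is larger still.
- **The pairwise benchmark is the reviewer's.** True. With a pooled error term the proportion of allocations in which the weakest comparison is below 0.80 is 23% instead of 25%. The average for the weakest comparison, 0.830, also stays above 0.80. The cost is in the tail.
- **Twelve is not a floor for each arm, nine is not a threshold in the plan, and equal allocation does not guarantee 12 completers.** All true. The completer figures show how much of the shortfall the fix removes and are not a pass mark.

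**Conclusion.** The concern holds. The stated allocation rule, followed as written, does not deliver the stated arm sizes, and nothing else in the protocol resolves this.

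Read literally, the design meets its own 15 per arm about once in 467 allocations. The overall test gives up at most 0.894 − 0.878 = 0.016 in average power. The weakest comparison with D gives up 0.907 − 0.830 = 0.077 on average, with about a one-in-four chance of dropping below 0.80. The pairwise figures rest on the assumed reference effect and on independent assignment with equal probabilities; the completer figures rest on 20% dropout. Read loosely, the power cost is zero and the defect is a wrong label.

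This should be fixed: the inconsistency is certain, the possible loss is modest to moderate, and correction costs almost nothing.

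**What to change.** Replace the reference to simple randomisation with a restricted scheme that yields 15 per arm. Either of these will do:

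- a concealed, computer-generated list with 15 places per arm in random order; or
- permuted blocks of randomly varying size that together total 60, with the block sizes kept out of the protocol and not disclosed to recruiters.

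The first is sufficient to remove the contradiction. State that the list is prepared before the first enrolment by a person who is not a trial participant and has no part in recruitment, training or testing; this also corrects the slip noted above. Keep the envelopes as planned.

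Stratifying by club is optional. If it is used, incomplete blocks within a club may leave arms slightly off 15, and club should then enter the model at a cost of one degree of freedom.

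The cost is one sentence and a different list, with no extra players, visits or tests. The documents do not give the enrolment status. If allocation has already begun, the protocol should instead describe the method actually used.
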